7.2.1.4 Prior or Concomitant Medication

Medications will be coded according to the WHO Drug Dictionary (WHO-DD) B3 MAR 2019 version.

(1) Prior Medication

Prior medications are defined as any medication taken within 1 month before the start date of study drug.

Any prior medication, including prescription and over-the-counter medications, taken within 1 month before Screening will be recorded on the eCRF. Information recorded will include: name of medication, dose, duration of and reason for use. It should be noted if subjects have ever used afamelanotide.

(2) Concomitant Medication

Concomitant medication is defined as any medication, other than study medication, which is taken during the study after the start date of study drug , including prescription, over-the-counter medications, herbals, dietary supplements, and recreational drugs. All concomitant medications taken while the subject is participating in the study will be recorded. Concomitant medication will be given only if deemed necessary by the Investigator or the subject's personal physician.

Rules to determine prior medications and concomitant medications:

Medications with a stop date before the first date of study drug dosing will be considered prior medications. Medications with start date or stop date on or after the first date of study drug dosing or ongoing at study will be considered concomitant medications.

Rule to determine concomitant medication for pain:

If indication in the eCRF for the concomitant medications includes “Pain” or “pain”, the drug was regarded as comitant use for pain.

7.2.1.5 Treatment Duration and Compliance

(1) Treatment Duration

For DBT period, treatment duration (days) = end of treatment date in DBT period – first treatment date + 1

For DBE period, treatment duration (days) = end of treatment date in DBE period – first treatment date in DBE period + 1

The time period of treatment duration is as below;

- 1 <= - <= 29 (days)
- 29 < - <= 85 (days)
- 85 < - <= 183 (days)
- >183 (days)

For subjects lost to follow up, the treatment end date is taken to be the date of their last visit in the treatment periods. Interruptions and dose changes are not taken into account for treatment duration.

(2) Treatment Compliance

Treatment compliance will be calculated using the formula below and reported to 1dp by treatment periods. Interruptions and dose changes are not taken into account for treatment duration.

$$\frac{\text{Treatment duration (days)} - \text{number of days subject miss the medication}}{\text{Treatment duration (days)}} \times 100\%$$

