11.1.2 Study Drug Supply

The Sponsor will provide MT-7117 and placebo [REDACTED] in [REDACTED] to each site, for each subject, for the duration of their participation in the study. The Interactive Web-based Response System (IWRS) will allocate sufficient uniquely-numbered, blinded [REDACTED], to be dispensed by the Investigator, study nurse or hospital pharmacist, according to the subject's randomized treatment group (MT-7117 [REDACTED], [REDACTED], or placebo) and study visits. Each subject will take 2 [REDACTED] per day with or without food.

Subjects will be instructed to bring their study medication with them to each visit. Subjects will return all study medication that may remain in their possession to the study staff at the end of treatment visit. In cases where subjects forget to return to the clinic with their [REDACTED], sites will be instructed to inquire as to the subjects daily dosing compliance, capturing total number of days missed. Subjects will be instructed to return medication packaging and empty [REDACTED] at the follow up visit.

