11.3 Compliance

The prescribed dosage, timing, and mode of administration of study medication will not be changed. Subjects will be asked questions regarding the compliance, any departures from the intended regimen will be recorded in the eCRF.

Study medication accountability and subject compliance will be documented throughout the double-blind treatment period using study-specific study medication dispensing and return record forms. For subjects who do not return their █, the site will question each to determine compliance (e.g. number of doses missed since the last visit).

Subjects will be asked to return all unused medication including empty and partially used █. Study medication dispensed at the previous visit will be retrieved by the Investigator or designee and compliance assessed by returned medication count.

Non-compliance will be defined as taking $\leq 80\%$ or $\geq 120\%$ of study medication during any evaluation period (from any visit to the following visit).

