8.1.9 Treatment Duration and Compliance

Treatment duration will be summarized on the ITT1 and ITT2 populations.

Treatment duration and compliance will be listed on the RAND population. Study drug interruptions will be listed on the RAND population.

Compliance to Double-Blind study medication will be presented for the ITT1 and ITT2 population in table by treatment group. The range $80\% \leq \text{compliance} \leq 120\%$ will be used to define a subject being treatment compliant.

The number and percentage of subjects with no study drug suspension, any study drug suspension and permanent study drug discontinuation will be summarized by the DBT period on the ITT1 population and by the DBE period on the ITT2 population.

All study medication administration and accountability data will be listed by subject.

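### The SAP's compliance ratio cannot exceed 100% and is taken once per treatment period, so its 120% limit has no effect and its compliance table departs from the protocol's definition of non-compliance

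*SAP*

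**What the plan says.** **SAP.** Section 7.2.1.5 takes treatment duration in days, subtracts the "number of days subject miss the medication", and divides by treatment duration. The result is "reported to 1dp by treatment periods", so a subject has one value for the double-blind period and one for the extension. The section adds: "Interruptions and dose changes are not taken into account for treatment duration". Section 8.1.9 tabulates compliance by arm; the range from 80% to 120%, both ends included, "will be used to define a subject being treatment compliant". Section 10 declares no departure from the protocol's analyses.

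**Protocol.** Section 11.3 has "compliance assessed by returned medication count". Non-compliance means taking 80% or less, or 120% or more, "of study medication during any evaluation period (from any visit to the following visit". Section 11.1.2 sets the daily amount ("Each subject will take 2"; the unit is redacted). Where subjects do not bring their medication back, sites ask about dosing, "capturing total number of days missed". Days missed is therefore the protocol's fallback measure, and the count is its main one.

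**The concern.** The two documents use the same two percentages for different quantities. The protocol's 120% limit makes sense for a unit count, which can exceed what was due. Attached to a ratio of days it does nothing. The time unit differs as well: the protocol tests each visit-to-visit period, while the SAP averages over about 26 weeks, so a complete gap in one interval can be diluted until it passes. The treatment of exactly 80% is also reversed.

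At stake is the by-arm compliance table in a trial with two active doses and placebo. A reader who sees an 80% to 120% range will assume that it applies the protocol definition. For missed dosing the difference runs in one direction: the table will tend to show higher compliance than the protocol rule would. Over-dosing cannot appear in it at all.

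**Working it through.** The documents report no calculated compliance figure, so there is nothing to reproduce first. The check applies the SAP formula directly and compares it with the protocol measure.

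**Inputs**
- SAP formula: C = 100 × (T − m)/T, with T = treatment duration and m = days missed (SAP 7.2.1.5).
- T = 182 days for a completed double-blind period (SAP Table 2); 183 was also tried.
- Nominal visit days 1, 15, 29, 57, 85 and 183 (Protocol Table 9-1), giving intervals of 14, 14, 28, 28 and 98 days.
- Two units due per day (Protocol 11.1.2).
- Assumptions: a missed day is a day with no dose, interruption days count as missed, and all other doses are taken in full.

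**1. Range of the ratio.** Since m ≥ 0, C is largest at m = 0: 100 × 182/182 = 100%. A value of 120% would need m = −36.4 days.

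**2. Missed days that still pass.**
- m = 36: 146/182 = 80.2%, compliant.
- m = 37: 145/182 = 79.7%, not compliant.
- With T = 183 the limit is the same: 147/183 = 80.3% and 146/183 = 79.8%.

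**3. Interval value against SAP value.** Every row is non-compliant under Protocol 11.3 and compliant under SAP 8.1.9. The last three rows are the smallest numbers of missed days that breach the protocol rule in each interval length.

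| Days missed | Interval value | SAP value |
|---|---|---|
| All 28, Visit 4 to 5 (Days 29–57) | 0/28 = 0% | 154/182 = 84.6% |
| 36 of 98, Visit 6 to 7 (Days 85–183) | 62/98 = 63.3% | 146/182 = 80.2% |
| 3 of 14 | 11/14 = 78.6% | 179/182 = 98.4% |
| 6 of 28 | 22/28 = 78.6% | 176/182 = 96.7% |
| 20 of 98 | 78/98 = 79.6% | 162/182 = 89.0% |

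Visit 5 may be a mobile sampling visit. If medication is counted only at Visits 4 and 6, the first row becomes 28/56 = 50%, still non-compliant under the protocol.

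**4. Boundary.** A subject treated for 180 days with 36 missed scores 144/180 = 80.0% exactly. That value is compliant in SAP 8.1.9; the same percentage is non-compliant in Protocol 11.3.

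**5. Units rather than days.**
- Four units daily throughout: by count 728/364 = 200%; SAP (182 − 0)/182 = 100%.
- One unit daily throughout: by count 182/364 = 50%. The SAP gives 100% if a partly taken day is not a missed day, and 0% if it is. The SAP does not say which.

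**6. Interruptions.** SAP 7.2.1.5 keeps interruption days in T but does not say whether they enter m. Protocol 10.9.4 (suspicious nevi) and 12.3.1 (hepatic events of special interest) both foresee suspended dosing. If those days are not counted in m, an interruption of any length could score 100%.

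**The case against.** The strongest reply is that little depends on this table.
- No analysis population in SAP section 5 uses the percentage, and efficacy is analysed by randomized treatment under a treatment-policy estimand.
- The subgroup in SAP 8.2.1 that is named for study drug compliance is built on suspension and discontinuation, not on this ratio.
- SAP 8.1.9 also lists administration, accountability and interruptions, and tabulates suspension and permanent discontinuation. Protocol 12.11 requires any overdose to be reported as an adverse event.

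All of this stands. A reader might infer that the trial cannot show under-dosing or over-dosing, or that the efficacy comparison is at risk. The documents support neither inference.

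A reader might also be drawn to the first four weeks as the example, with no drug taken between Visits 2 and 4. That does not work. Duration starts at the first treatment date, so a subject who first dosed on Day 29 would have T = 154 and score 100%. Visit 3 also lies between, so this is not one protocol interval. The gap between Visits 4 and 5 avoids both problems.

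It can further be said that Protocol 11.3 is a conduct section, that protocol section 14 specifies no compliance analysis, and that SAP section 1 gives the SAP precedence on statistical detail. This weakens the complaint about section 10. It does not help with the 120% limit, because the formula and the limit are both SAP text.

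**Conclusion.** The definition is wrong as written, with limited consequence. The upper limit cannot be reached, and the measure, the interval and the 80% boundary all differ from Protocol 11.3 without a declared change. In a full 182-day period, up to 36 missed days are tabulated as compliant, including a complete 28-day gap between Visits 4 and 5.

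The 36-day limit assumes that interruption days count as missed; on that reading, gaps of 37 days or more are flagged. The 100% score for daily half-dosing is conditional on how a partly taken day is counted, so it should not be stated as a fact of the plan. The documents do not say how many subjects would be reclassified.

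The effect is confined to a descriptive table. This is a correction worth making, minor to moderate in weight, and it does not bear on the primary or secondary inferences.

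**What to change.** **SAP 7.2.1.5.** Compute units taken divided by units due, from returned counts, for each visit-to-visit interval at which accountability is done. Use site-recorded missed doses where packs are not returned. State how partly taken days and protocol-directed interruption days are counted, and show compliance with and without the interruption days, so that a hold required by the protocol is not read as poor adherence.

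**SAP 8.1.9.** Classify a subject as non-compliant if any interval is at or below 80% or at or above 120%, as in Protocol 11.3. Also show overall compliance by arm.

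**Minimum alternative.** Keep the day-based ratio, remove the 120% limit, align the 80% boundary, and declare the departure from Protocol 11.3 in SAP section 10.

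**Cost.** SAP wording and programming; accountability data are already collected and listed. The reported compliance rate may be lower. A unit count measures units taken, not active dose; how each arm's daily units are made up is redacted, so the table should be labelled accordingly.

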7.2.2 Efficacy assessments

7.2.2.1 The Sunrise and Sunset Time to Use

The primary and some secondary efficacy endpoints are derived from the diary data. The sunlight exposure time between 1 hour post sunrise and 1 hour pre-sunset will be used. For the subjects exposed to sunlight, the sunrise and sunset times will be calculated for the corresponding country or geographical area. If the subjects exposed themselves while based in the US, the sunrise and sunset times for the corresponding US state, federal district, islands, or territory will be used.

To calculate sunrise and sunset times anywhere in the world, we will use the algorithms published by the National Oceanic and Atmospheric Administration (<https://www.esrl.noaa.gov/gmd/grad/solcalc/calcdetails.htm>).

During the ongoing study, the subjects' geographical locations for sunlight exposure will be reviewed from time to time. The sunrise and sunset time for the US locations, other countries, cities, and geographical areas will be added into SDTM as needed. The last time new sunrise and sunset time will be added is 5 weeks before the last subject last visit in the study. In the event that a subject had sun exposure while being in the location for which no sunrise and sunset time is readily available, the time 6:00 and 18:00 will be used as sunrise and sunset time. This is a close approximation of the average sunrise and sunset time for the current accumulated study data in the US.

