7.3 Analysis Visit Definitions

(1) eDiary data excluding in-clinic sunlight exposure test

The subjects will, in their diaries, record the sunlight exposure periods (start/end time), prodromal symptom periods, and pain periods. The subjects' sunlight exposure start and end times will be compared with their state capital cities sunrise and sunset times.

The analysis windows are defined in the table below. The nominal day for each week relative to the first dose day will be used. Day 1 is the first dose day.

Table 2 Analysis Visit Window for diary data

Analysis Visit	Nominal day	Analysis Visit Window for DBT analysis
Baseline*	Day 1	Day -14 to -1
Week 2	Day 15	Day 1 to 14
Week 4	Day 29	Day 15 to 28
Week 6	Day 43	Day 29 to 42
Week 8	Day 57	Day 43 to 56
Week 10	Day 71	Day 57 to 70
Week 12	Day 85	Day 71 to 84
Week 14	Day 99	Day 85 to 98
Week 16	Day 113	Day 99 to 112
Week 18	Day 127	Day 113 to 126
Week 20	Day 141	Day 127 to 140
Week 22	Day 155	Day 141 to 154
Week 24	Day 169	Day 155 to 168
Week 26 (DBT EOT)	Day 183	Day 169 to 182
Week 26 (DBE Baseline)	Day 183	Day 169 to 182
Week 28	Day 197	Day 183 to 196
Week 32	Day 225	Day 211 to 224
Week 39	Day 274	Day 260 to 273
Week 52 (DBE EOT)	Day 365	Day 351 to 364
EOT for DBT	Day 182 or discontinued during DBT	14 days before EOT for DBT
EOT for DBE	Day 365 or discontinued during DBE	14 days before EOT for DBE
Follow-up until Week 32 (DBT EOS)	6 weeks after EOT for DBT	the latest 1 to 14 days before Follow-up date not overlapping with treatment duration in DBT period
Follow-up until Week 58 (DBE EOS)	6 weeks after EOT for DBE	the latest 1 to 14 days before Follow-up date not overlapping with treatment duration in DBE period

During 26 weeks (DBT)	1 to 182	Day 1 to EOT for DBT period
During 26 weeks (DBE)	183 to 364	DBE Baseline to EOT for DBE period

* If subjects have at least 1 day between Day -1 and Day -14, the baseline value will be calculated from the data between Day -1 and Day -14. If subjects have no data of sunlight exposure between Day -1 and Day -14, then the Analysis Visit window will be expanded to Day -28 and the baseline value will be calculated from the data between Day -1 and Day -28.

(2) Non-diary data including in-clinic sunlight exposure test

Table 3 Analysis Visit Window for non-diary efficacy data

Analysis Visit	Nominal day	Analysis Visit Window
Baseline	First dose day	NA
Week 4	Day 29	Day 16 to 64
Week 12	Day 85	Day 72 to 119
Week 26 (DBT EOT)	Day 183	Day 134 to 202

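### Diary days at locations without a loaded sunrise time get a fixed 6:00–18:00 day, although the SAP already adopts an algorithm that works anywhere; a small, avoidable source of noise in the primary endpoint

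*SAP*

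**What the plan says.** The primary endpoint counts only sunlight exposure between 1 hour after sunrise and 1 hour before sunset. SAP 7.2.2.3.1 applies this as step 1 of the derivation and drops exposure outside the interval.

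SAP 7.2.2.1 says where the sunrise and sunset times come from:

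- Main rule: "the sunrise and sunset times will be calculated for the corresponding country or geographical area". Within the US, the state, federal district, island or territory is used.
- Method: "To calculate sunrise and sunset times anywhere in the world, we will use the algorithms published by the National Oceanic and Atmospheric Administration".
- Maintenance: subjects' locations are reviewed during the study, and times for US locations, "other countries, cities, and geographical areas will be added into SDTM as needed". Additions stop 5 weeks before the last subject's last visit in the study.
- Fallback: "the time 6:00 and 18:00 will be used as sunrise and sunset time" whenever a subject's exposure took place "in the location for which no sunrise and sunset time is readily available". The reason given is: "This is a close approximation of the average sunrise and sunset time for the current accumulated study data in the US".

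SAP 7.3 describes the reference place differently. There, the subjects' exposure times "will be compared with their state capital cities sunrise and sunset times".

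**The concern.** The fallback ignores calendar date and latitude, and its only support is an average over US data. The trial runs in ten countries, including Norway and Sweden (SAP 8.1.5), and subjects may also record exposure while travelling elsewhere. If the place is known well enough to tell that it is not on the list, the algorithm already adopted can be run for it, and the constant is not needed.

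The fallback also reaches the 66-minute responder endpoint, which is built on the same variable, and the total-time endpoints that reuse step 1 (SAP 7.2.2.3.5). The SAP plans no count or flag of fallback days and no sensitivity analysis of them. Separately, a programmer reading 7.2.2.1 and 7.3 together finds two descriptions of the reference place.

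**Working it through.** **The plan's own figure.** The 6:00/18:00 average rests on accumulated study data that the documents do not show, so it cannot be reproduced. As a rough comparison only, calendar-year averages on the civil clock, with summer time, for five US cities (New York, San Francisco, Houston, Chicago, Miami; coordinates assumed) give mean sunrise between 06:23 and 06:56 and mean sunset between 18:36 and 19:06. These are not weighted by the study's diary days, so they neither confirm nor refute the statement.

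**Inputs.** Fallback times 6:00 and 18:00 (SAP 7.2.2.1). One hour trimmed at each end (SAP 7.2.2.3.1). Latitudes are an assumption, because the documents give none; 30–60 degrees is shown. Times are local solar time.

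**Fallback window.** 7:00 to 17:00 = 10 h.

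**True window.** With latitude φ and solar declination δ, the sunrise hour angle H satisfies

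cos H = cos(90.833°) / (cos φ · cos δ) − tan φ · tan δ

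Day length = 2H/15 h, and the counted window = day length − 2 h.

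Example, 60 degrees, 21 June (δ = 23.45°): cos H = −0.783, H = 141.5°, day length 18.87 h, window 16.87 h. The fallback drops 16.87 − 10 = 6.87 h.

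Example, 60 degrees, 21 December (δ = −23.42°): cos H = 0.719, H = 44.1°, day length 5.88 h, window 3.88 h. The fallback adds 10 − 3.88 = 6.12 h.

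| Latitude | True window, 21 June | Dropped by fallback | True window, 21 Dec | Added by fallback | Error, 20 Mar / 22 Sep |
|---|---|---|---|---|---|
| 30° | 12.1 h | 2.1 h | 8.2 h | 1.8 h | 0.1 / 0.2 h |
| 40° | 13.0 h | 3.0 h | 7.3 h | 2.7 h | 0.1 / 0.2 h |
| 50° | 14.4 h | 4.4 h | 6.1 h | 3.9 h | 0.1 / 0.3 h |
| 60° | 16.9 h | 6.9 h | 3.9 h | 6.1 h | 0.1 / 0.4 h |

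Dates are for the northern hemisphere. Civil-clock offsets move the error towards one end of the day and can change it somewhat. For Madrid on 21 June, for example, the clock-time result is 3.8 h dropped and 0.7 h added.

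**From window to endpoint.** The endpoint is the mean over qualified days in a 14-day window. With 14 qualified days:

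- one fallback day with 60 misplaced minutes of recorded exposure: 60/14 = 4.3 min;
- one fallback day at the extreme, with all 6.87 h recorded as symptom-free exposure: 6.87 × 60/14 = 29 min.

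For scale, the planned difference is 57 min and the SD 79.3 min (SAP 3.3). SAP 7.2.2.3.1 asks for only one qualified day per window, so in a sparse diary a single fallback day can be the whole value.

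**Which days can be affected.** If the last visit in the study is Week 58 (SAP 4.2), or Week 32 without the extension, additions stop at Week 53 or Week 27. Both fall after the Week 26 diary window (Days 169–182). If the last double-blind visit (Day 183) is meant, they stop at Day 183 − 35 = 148 of the last subject. On either reading every subject's baseline (Days −14 to −1) precedes the cut-off, so its locations could still be added.

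**The case against.** The strongest reply is that this is an edge case. The main rule covers the countries where subjects live, locations are reviewed and added as needed, and the fallback touches only what is left. The rule is blind to arm in a randomised, double-blind trial with region as a stratification factor. This stands, and it keeps the point small.

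A reader might infer three stronger things that the documents do not support:

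- *Exposure at high-latitude sites is cut or inflated by hours.* Norway, Sweden, the UK, Germany and Canada are trial countries, and the main rule calculates their times. The fallback applies to unlisted places, mainly travel.
- *The error runs in opposite directions at baseline and Week 26.* That needs the same subject to have fallback days in both windows near opposite solstices. Because baseline precedes the cut-off on any reading, its locations could still have been loaded.
- *The study site's coordinates are the obvious replacement.* For a distant traveller they can be worse. Take a subject from 60 degrees visiting 30 degrees. In June the true window is 12.1 h; the fallback errs by 2.1 h and the site window by 16.9 − 12.1 = 4.8 h. In December the true window is 8.2 h; the fallback errs by 1.8 h and the site window by 8.2 − 3.9 = 4.3 h.

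On the reference place, the capital city may simply be the point used to represent a US state. That is plausible for the US but leaves other countries undefined, so a clarifying sentence is still needed.

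**Conclusion.** The point holds in a limited form. The fallback is a stated rule that produces a wrong eligibility window on the days it touches, and the same section already contains the means to avoid it. The window error ranges from negligible near the equinoxes to several hours near the solstices, and it is not confined to high latitudes: at 40 degrees it is already about 3 h in June. The hours describe window width and are not endpoint changes.

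The likely result is added noise. Some dilution is possible if subjects on active drug spend longer outdoors and early or late summer exposure is clipped. Nothing in the documents shows a bias in favour of either arm. The conclusion rests on assumed latitudes, on solar rather than clock time, and on an unknown number of fallback days. It is worth correcting because correction is cheap, not because the primary result is at risk.

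**What to change.** 1. Before each database lock, run the adopted algorithm for every recorded exposure location and calendar date, with no earlier cut-off for adding places.
2. Only where the location is unknown, use the subject's site or home area for that date in place of 6:00/18:00.
3. Report the number of diary days handled under item 2 by arm.
4. State one reference-point rule, identically, in SAP 7.2.2.1 and 7.3, covering both US states and other countries.

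The cost is a little extra programming and one clarifying sentence. No new data need to be collected.
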